## 1. RCT Details

This section provides a high-level overview of an RCT that the described real-world evidence study is trying to replicate as closely as possible given the remaining limitations inherent in the healthcare databases.

### 1.1 Title

**Angiotensin-Neprilysin Inhibition versus Enalapril in Heart Failure ([PARADIGM-HF trial](#))**

### 1.2 Intended aim(s)

The primary objective of the study is to determine LCZ696 200 mg twice daily, a combination of sacubitril/valsartan, is superior to enalapril 10 mg twice daily in reducing the composite endpoint in place of Angiotensin Converting Enzyme inhibitors (ACEi) and Angiotensin II receptor blockers (ARBs)

### 1.3 Primary endpoint for replication and RCT finding

Composite endpoint of death from cardiovascular (CV) causes or hospitalization for heart failure (HF)

### 1.4 Required power for primary endpoint and noninferiority margin (if applicable)

After following 8000 patients for 34 months, at an overall two-sided alpha level of 0.05, the primary end point would occur in 2410 patients, which would provide a power of 97% to detect a 15% reduction in the risk of this outcome.

### 1.5 Trial estimate

HR = 0.80 (95% CI 0.73–0.87) comparing LCZ696 to enalapril (McMurry et al., 2014, NEJM)

## 3. Data Source(s)

Optum Clininformatics Data Mart, IBM MarketScan, Medicare

## 4. Study Design Diagram

The study design diagram visualizes key aspects of the longitudinal study design for expedited review  
**Design Diagram – PARADIGM-HF TRIAL REPLICATION**

## 5. Cohort Identification

### 5.1 Cohort Summary

This study will involve a new user, parallel group retrospective cohort study design comparing sacubitril/valsartan to ACE inhibitors. Although the trial compared sacubitril/valsartan to enalapril, we expanded the definition of the comparator group to include all ACEi therapies to improve power, since all medications within this class of medication are indicated and guideline recommended for use in heart failure with reduced ejection fraction patients and would be expected to have similar effects on the primary outcome of CV death and HF hospitalization.

The patients will be required to have continuous enrollment during the baseline period of 180 days before initiation of sacubitril/valsartan or a ACEi (cohort entry).

### 5.2 Important steps for cohort formation

New users (defined as no use of sacubitril/valsartan in 180 days prior to index date) of the exposure will be identified. New users of a comparator drug were identified as patients with no ACEi fills during the 60 days prior to the index date to allow for patients who are switching among ACEi drugs or restarting ACEi after a brief lapse.

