### 5.3 Flowchart of the study cohort assembly

	Optum		MarketScan		Medicare*	
	Less Excluded Patients	Remaining Patients	Less Excluded Patients	Remaining Patients	Less Excluded Patients	Remaining Patients
All patients		77,673,639		200,203,908		23,466,175
Did not meet cohort entry criteria	-73,445,846	4,227,793	-196,533,760	3,670,148	-18,348,713	5,117,462
Excluded due to insufficient enrollment	-623,954	3,603,839	-340,051	3,330,097	-1,288,867	3,828,595
Excluded due to prior use of referent	-3,168,921	434,918	-2,967,886	362,211	-3,495,789	332,806
Excluded due to prior use of exposure	-29,778	405,140	-12,511	349,700	-33,013	299,793
Excluded because patient qualified in >1 exposure category	-8	405,132	-3	349,697	-9	299,784
Excluded based on Age	0	405,132	-1	349,696	0	299,784
Excluded based on Gender	-39	405,093	0	349,696	0	299,784
Excluded based on Inclusion #1 - Age >=18 years old	-624	404,469	-1,354	348,342	-721	299,063
Inclusion #3 - HFpEF prediction algorithm applied to reference group†	-381,531	22,938	-337,242	11,100	-259,816	39,247
Excluded based on Inclusion #4b - Hospitalization for HF within the last 12 months	-9,321	13,617	-4,618	6,482	-10,685	28,562
Excluded based on Inclusion #5a - ACEis or ARBs	-1,224	12,393	-385	6,097	-1,534	27,028
Excluded based on Inclusion #5b - Beta-blockers	-673	11,720	-248	5,849	-2,128	24,900
Excluded based on Exclusion #3 - Known history of angioedema	-56	11,664	-29	5,820	-200	24,700
Excluded based on Exclusion #4 - Treatment with both ACEis AND ARBs	-15	11,649	-9	5,811	-34	24,666
Excluded based on Exclusion #5 - Acute decompensated HF	-1,060	10,589	-435	5,376	-5,457	19,209
Excluded based on Exclusion #6 - Symptomatic hypotension	-734	9,855	-240	5,136	-1,964	17,245
Excluded based on Exclusion #7 - Low eGFR / renal dysfunction	-1,064	8,791	-403	4,733	-2,833	14,412
Excluded based on Exclusion #8 - Hyperkalemia	-57	8,734	-14	4,719	-116	14,296
Excluded based on Exclusion #9 - ACS, Stroke, TIA, CABG, PCI, Other CV Procedures, Carotid Angioplasty	-765	7,969	-546	4,173	-2,912	11,384
Excluded based on Exclusion #11 - Implantation of CRT device	-41	7,928	-19	4,154	-1,550	9,834
Excluded based on Exclusion #12 - History of heart transplant or LVAD	-56	7,872	-33	4,121	-35	9,799
Excluded based on Exclusion #13 - History of severe pulmonary disease	-463	7,409	-205	3,916	-1,029	8,770
Excluded based on Exclusion #14 - Diagnosis of peripartum- or chemotherapy-induced cardiomyopathy	-38	7,371	-34	3,882	-60	8,710

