3	LVEF ≤ 35%	
Measured 180 days prior to and including the day of index drug initiation in any diagnosis position and inpatient or outpatient care setting
 
Systolic Heart Failure
 
ICD-9 diagnosis: 428.2x
 
ICD-10 diagnosis: I50.2x
 
Combined Systolic/Diastolic Heart Failure
 
ICD-9 diagnosis: 428.4x
 
ICD-10 diagnosis: I50.4x
		
4	Plasma BNP ≥150 pg/mL or NT-proBNP ≥600 pg/mL at the screening visit and a hospitalization for HF within the last 12 months			
4a	Plasma BNP ≥150 pg/mL or NT-proBNP ≥600 pg/mL at the screening visit			
AND the following:				

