# Appendix A

		Measured 365 days prior to drug initiation in any diagnosis position and inpatient care setting	
4b	Hospitalization for heart failure within the last 12 months	
Hospital Admission for CHF
 
ICD-9 diagnosis: 428.x, 398.91, 402.01, 402.11, 402.91, 404.01, 404.11, 404.91, 404.03, 404.13, 404.93
 
ICD-10 diagnosis: I50.1, I50.2x, I50.4, I50.814, I09.81, I11.0, I13.0, I13.2
	
5	Treatment with a stable dose of an ACE inhibitor or an ARB equivalent to enalapril 10 mg/day for at least 4 weeks before the screening visit; and treatment with a stable dose of a beta-blocker for at least 4 weeks prior to the screening visit, unless contraindicated or not tolerated	
Measured 47 days to 2 days prior to drug initiation in prescription claims requiring 28 days supply of oral ACEi or ARB -
 
ACE inhibitors' generic names for prescription claims: Enalapril, Captopril, Clazapril, Fosinopril, Lisinopril, Moexipril, Perindopril, Quinapril, Trandolapril, Zofenopril, Benazepril
 
-OR-
 
ARBs generic names for prescription claims: Candesartan, Eprosartan, Irbesartan, Losartan, Olmesartan, Telmisartan, Valsartan, Azilsartan
	
5a	Treatment with a stable dose of an ACE inhibitor or an ARB equivalent to enalapril 10 mg/day for at least 4 weeks before the screening visit	AND the following:	
5b	Treatment with a stable dose of a beta-blocker for at least 4 weeks prior to the screening visit, unless contraindicated or not tolerated	
Measured 45 days prior to index drug initiation in prescription claims (generic names) of an oral beta-blocker for at least 4 weeks (28 days)
 
Beta-blocker generic names for prescription claims: Acebutolol, Atenolol, Betaxolol, Bisoprolol, Carvedilol, Esmolol, Labetalol, Metoprolol, Metiranolol, Nebivolol, Nadolol, Propranolol, Pindolol, Sotalol, Penbutolol, Oxprenolol
	
6	Although not required, the protocol specified that an aldosterone antagonist should also be considered in all patients, taking account of renal function, serum potassium, and tolerability. If given, the dose of aldosterone antagonist should be stable for at least 4 weeks prior to the screening visit		
EXCLUSION CRITERIA			

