1	History of hypersensitivity or allergy to any of the study drugs, drugs of similar chemical classes, ACE inhibitors (ACEIs), ARBs, or neprilysin inhibitors, as well as known or suspected contraindications to the study drugs		
2	Previous history of intolerance to recommended target doses of ACEIs or ARBs		
3	Known history of angioedema	
Measured from the start of all available data to index drug initiation in any diagnosis position and inpatient or outpatient care setting
 
ICD-9 diagnosis: 995.1 ICD-10 diagnosis: T78.3x
	
4	Requirement for treatment with both ACEIs and ARBs	
Measured 180 days prior to and including day of drug initiation in prescription claims (generic names) for any of oral ACEi and ARB for two subsequent dispensings
 
ACE inhibitors' generic names for prescription claims: Enalapril, Captopril, Clazapril, Fosinopril, Lisinopril, Moexipril, Perindopril, Quinapril, Ramipril, Trandolapril, Zofenopril, Benazepril
 
-AND-
 
ARBs generic names for prescription claims: Candesartan, Eprosartan, Irbesartan, Losartan, Olmesartan, Telmisartan, Valsartan, Azilsartan
	
5	Current acute decompensated heart failure (exacerbation of chronic heart failure manifested by signs and symptoms that may require intravenous therapy)	
Measured 7 days prior to and including day of drug initiation in any diagnosis position and inpatient and emergency care setting
 
ICD-9 diagnosis: 428.41, 428.43 ICD-10 diagnosis: I50.23, I50.41, I50.43
	
6	Symptomatic hypotension and/or a systolic blood pressure <100 mmHg at Visit 1 (screening) or <95 mmHg at Visit 3 or at Visit 5 (randomization)	
Measured 30 days prior to and including day of drug initiation in any diagnosis position and inpatient or outpatient care setting
 
Hypotension: ICD-9 diagnosis: 458.xx, 785.5x ICD-10 diagnosis: I95.xx, R57.xx
	

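### The comparator eligibility rules conflict with one another as written, and the cohort that was matched is not the one the flowchart describes

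*Protocol*

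**What the plan says.** - **Washout (5.2).** "New users of a comparator drug were identified as patients with no ACEi fills during the 60 days prior to the index date" The stated purpose is "to allow for patients who are switching among ACEi drugs or restarting ACEi after a brief lapse". The flowchart in 5.3 has a matching row, "Excluded due to prior use of referent".
- **Prior treatment (Appendix A, Inclusion #5a).** "Measured 47 days to 2 days prior to drug initiation in prescription claims requiring 28 days supply of" an oral ACEi or ARB. No arm is named. Section 6.1 explains that patients need be new users of their own group's drug only, because the trial required earlier ACEi or ARB treatment.
- **Drug lists (Appendix A).** Inclusion #5a lists "Enalapril, Captopril, Clazapril, Fosinopril, Lisinopril, Moexipril, Perindopril, Quinapril, Trandolapril, Zofenopril, Benazepril". Exclusion #4 lists "Enalapril, Captopril, Clazapril, Fosinopril, Lisinopril, Moexipril, Perindopril, Quinapril, Ramipril, Trandolapril, Zofenopril, Benazepril". The ejection-fraction algorithm's ACEi term also includes ramipril.
- **Ejection fraction.** The only such row in 5.3 is "Inclusion #3 - HFpEF prediction algorithm applied to reference group". Appendix A, Inclusion #3, instead uses systolic or combined heart-failure codes, "Measured 180 days prior to and including the day of index drug initiation in any diagnosis position and inpatient or outpatient care setting", and names no arm.
- **Cohort.** The flowchart totals equal the Section 7 cohort. Section 9 then describes completing the covariates and matching 1:1. Appendix B gives the arms before and after matching.

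**The concern.** A comparator arm should follow from its written rules. Here two programmers could build different reference arms, depending on whether #5a counts fill dates, covered days or active claims. The switchers named in 5.2 may be removed by the rule meant to let them in.

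Two further matters bear on what the matched comparison estimates. If the propensity score's ACEi covariate counts the index fill, it is true of every reference patient by construction, and exposed patients with prior ARB use only are lost because of how a covariate is measured. And if the matched cohort was not built by the flowchart, no reader can check which criteria were enforced in it, and the final power borrows its risk from another cohort.

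**Working it through.** **1. Washout against #5a.** Days -47 to -2 are a strict subset of days -60 to -1. An ACEi fill on day d with S days' supply covers d to d+S-1, and the washout requires d of -61 or earlier. Covered days inside the #5a window = min(d+S-1, -2) - max(d, -47) + 1.
- S = 30, d = -61: covers -61 to -32, so -47 to -32 = 16 days. This is the most a 30-day fill can give, so 28 is out of reach.
- S = 60: at least 28 days only for d = -79 to -61.
- S = 90: at least 28 days only for d = -109 to -61.
- If #5a counts fill dates, no ACEi fill can satisfy it in the reference arm; only an ARB can.
- The washout counts fills, not supply. A 90-day fill on days -90 to -61 runs to day -1 or later, yet the patient counts as a new user.

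**2. Ejection fraction.** The flowchart row uses a prediction algorithm and names one arm. Appendix A #3 uses diagnosis codes and names none. The method and the arm both differ.

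**3. Ramipril.** It is absent from one ACEi list and present in two. Programmed as listed, a patient whose only qualifying drug is ramipril fails #5a in either arm.

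**4. ACEi covariate** (Appendix B, database columns Optum + MarketScan + Medicare; the pooled count columns leave out MarketScan).
- Reference arm before matching: 100% in all three databases, although #5a has an ARB-only route.
- Exposed with ACEi use before matching: 1,288 + 764 + 1,018 = 3,070 of 2,424 + 1,289 + 1,658 = 5,371 (57.2%).
- Exposed after matching: 1,279 + 748 + 1,006 = 3,033, all with ACEi use.
- Exposed without ACEi use: 1,136 + 525 + 640 = 2,301, none matched.
- Lost in matching: 5,371 - 3,033 = 2,338, of whom 2,301 (98.4%) had no ACEi use and 3,070 - 3,033 = 37 had it.

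**5. Cohort size.**
- Section 7 reference: 4,217 + 2,218 + 6,293 = 12,728. Exposed: 2,729 + 1,476 + 1,738 = 5,943. Sum 18,671 = 6,946 + 3,694 + 8,031, the flowchart's final row.
- Appendix B reference: 17,244 + 10,721 + 18,303 = 46,268 (3.6 times as many). Exposed: 5,371 (fewer).
- Optum's 17,244 comparators alone exceed the 13,617 patients, both arms together, left after Inclusion #4b. MarketScan's 10,721 exceed 6,482. Adding covariates cannot enlarge an arm.
- Exclusion #13 bars pulmonary hypertension and other pulmonary heart disease over all available data. After matching, Appendix B still shows 250 + 132 + 209 = 591 of 3,033 reference (19.5%) and 257 + 126 + 223 = 606 of 3,033 exposed (20.0%).

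**6. Power.** Events = 2 x 3,033 x 0.21525 = 1,305.7. Power = Phi(sqrt(1,305.7)/2 x |ln 0.8| - 1.96) = 0.981, which reproduces the stated pooled figure. The risk is 4,019/18,671 = 0.21525, from the flowchart cohort. The matched cohort's risk is not given. Over an assumed range:

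| Assumed risk per 1,000 | Events | Power |
|---|---|---|
| 120 | 728 | 0.853 |
| 160 | 971 | 0.935 |
| 200 | 1,213 | 0.973 |
| 250 | 1,517 | 0.991 |

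**The case against.** Several stronger readings are tempting, and the document does not support them.

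- **That the washout and #5a exclude each other, or that all switchers are barred.** An ARB, or a longer ACEi supply filled before day -60, can meet both. Only switchers with an ACEi fill in the last 60 days are removed.
- **That the low ARB share in the reference arm before matching (570 + 340 + 804 = 1,714 of 46,268, 3.7%) shows the two rules were not enforced.** That is not the flowchart cohort, and carried-over ACEi supply could satisfy #5a. The flowchart's #5a row pools both arms and does not settle it either.
- **That ejection fraction was in fact screened in one arm only.** The flowchart is not exhaustive: Inclusion #2 and Exclusion #20 have no row either. What is shown is a conflict between two passages. The exposure drug's reduced-ejection-fraction indication may explain the label, but the document does not say so.
- **That the index fill explains the 100%.** The default window in 6.2 includes the index date, which makes this likely, but the covariate's own window is not stated.
- **That the pulmonary-hypertension counts prove the two cohorts used different rules.** The #13 row removes only 463/7,872 (5.9%), 205/4,121 (5.0%) and 1,029/9,799 (10.5%), so #13 may already have been narrower than written in the flowchart cohort. The counts show only that #13 as written was not enforced in the matched cohort.

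The design diagram and the external folder cited in Appendix A were not available for this check. They may hold arm-specific windows or a counting rule, which would soften steps 1 and 2. They cannot make 12,728 equal 46,268.

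**Conclusion.** The point holds as a set of contradictions within the protocol.

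Firmest is the cohort mismatch: 12,728 reference and 5,943 exposed patients in the flowchart against 46,268 and 5,371 entering the match. The containment of the #5a window within the no-fill period, the missing ramipril and the disagreement on ejection fraction can be read directly from the text. How many patients each affects, and the direction of any bias, cannot be derived.

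The loss of all 2,301 exposed patients without baseline ACEi use is a fact of Appendix B. Its cause is not settled: it may be an artefact of counting the index fill or a true lack of overlap. Either way, the matched comparison is narrower than the ACEi-or-ARB population that 6.1 describes.

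The power arithmetic is correct for its inputs, but the risk belongs to a different cohort. Over assumed risks of 120 to 250 per 1,000, pooled power runs from 0.853 to 0.991, so pooled power is probably not the main worry. This should be fixed before the results are interpreted.

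**What to change.** 1. Reconcile 5.2 with Inclusion #5a so that the switchers and restarters 5.2 names can meet both. One option is to apply the washout to the index ACEi only, requiring no recent fill and no supply on hand at index. State how #5a counts supply, in keeping with the four-week stable treatment it represents; a claim that merely touches the window would not be enough. With 28 covered days required, recent users of another ACEi then pass. Same-drug restarters relying on a single fill pass with 60-day fills on days -79 to -61 or 90-day fills on days -109 to -91, but not with a 30-day fill, so the text should say which lapses it means to admit.
2. Reconcile the flowchart row with Appendix A #3, state the arm for each ejection-fraction criterion, and apply the #3 codes to both arms as a sensitivity analysis.
3. Add ramipril to the #5a list.
4. Measure the propensity score's ACEi covariate before the index date, without the index fill, and state its window. If the 100% proves to be true prior use, state that the matched comparison covers prior ACEi users only.
5. Give the flowchart by arm, with its rules, for the cohort actually matched, and recompute power from that cohort's risk.

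Cost: wording in 5.2, 5.3 and Appendix A, and a re-run of cohort assembly, matching and power. Patient numbers and power may move either way, because reference-arm ACEi use before the index date is not reported. Stated final power by database is already only 0.73, 0.41 and 0.70 (Optum, MarketScan, Medicare).

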#### 5.2.1 Eligible cohort entry date

Sacubitril/valsartan was approved by FDA for market availability on July 7, 2015.

- Optum: July 7, 2015 – March 31, 2020 (end of data availability)
- Marketscan: July 7, 2015 – December 31, 2018 (end of data availability)
- Medicare: July 7, 2015 – December 31, 2017 (end of data availability)

#### 5.2.2 Specify inclusion/exclusion criteria for cohort entry and define the index date

Inclusion and exclusion criteria were adapted from the trial as closely as possible. Definitions for all inclusion/exclusion are provided in **Appendix A** and are summarized in the flowcharts below.

### 5.3 Flowchart of the study cohort assembly

	Optum		MarketScan		Medicare*	
	Less Excluded Patients	Remaining Patients	Less Excluded Patients	Remaining Patients	Less Excluded Patients	Remaining Patients
All patients		77,673,639		200,203,908		23,466,175
Did not meet cohort entry criteria	-73,445,846	4,227,793	-196,533,760	3,670,148	-18,348,713	5,117,462
Excluded due to insufficient enrollment	-623,954	3,603,839	-340,051	3,330,097	-1,288,867	3,828,595
Excluded due to prior use of referent	-3,168,921	434,918	-2,967,886	362,211	-3,495,789	332,806
Excluded due to prior use of exposure	-29,778	405,140	-12,511	349,700	-33,013	299,793
Excluded because patient qualified in >1 exposure category	-8	405,132	-3	349,697	-9	299,784
Excluded based on Age	0	405,132	-1	349,696	0	299,784
Excluded based on Gender	-39	405,093	0	349,696	0	299,784
Excluded based on Inclusion #1 - Age >=18 years old	-624	404,469	-1,354	348,342	-721	299,063
Inclusion #3 - HFpEF prediction algorithm applied to reference group†	-381,531	22,938	-337,242	11,100	-259,816	39,247
Excluded based on Inclusion #4b - Hospitalization for HF within the last 12 months	-9,321	13,617	-4,618	6,482	-10,685	28,562
Excluded based on Inclusion #5a - ACEis or ARBs	-1,224	12,393	-385	6,097	-1,534	27,028
Excluded based on Inclusion #5b - Beta-blockers	-673	11,720	-248	5,849	-2,128	24,900
Excluded based on Exclusion #3 - Known history of angioedema	-56	11,664	-29	5,820	-200	24,700
Excluded based on Exclusion #4 - Treatment with both ACEis AND ARBs	-15	11,649	-9	5,811	-34	24,666
Excluded based on Exclusion #5 - Acute decompensated HF	-1,060	10,589	-435	5,376	-5,457	19,209
Excluded based on Exclusion #6 - Symptomatic hypotension	-734	9,855	-240	5,136	-1,964	17,245
Excluded based on Exclusion #7 - Low eGFR / renal dysfunction	-1,064	8,791	-403	4,733	-2,833	14,412
Excluded based on Exclusion #8 - Hyperkalemia	-57	8,734	-14	4,719	-116	14,296
Excluded based on Exclusion #9 - ACS, Stroke, TIA, CABG, PCI, Other CV Procedures, Carotid Angioplasty	-765	7,969	-546	4,173	-2,912	11,384
Excluded based on Exclusion #11 - Implantation of CRT device	-41	7,928	-19	4,154	-1,550	9,834
Excluded based on Exclusion #12 - History of heart transplant or LVAD	-56	7,872	-33	4,121	-35	9,799
Excluded based on Exclusion #13 - History of severe pulmonary disease	-463	7,409	-205	3,916	-1,029	8,770
Excluded based on Exclusion #14 - Diagnosis of peripartum- or chemotherapy-induced cardiomyopathy	-38	7,371	-34	3,882	-60	8,710

Excluded based on Exclusion #15 - Documented untreated ventricular arrhythmia with syncopal episodes	-18	7,353	-6	3,876	-25	8,685
Excluded based on Exclusion #16 - Second- and third-degree AV block	-73	7,280	-29	3,847	-73	8,612
Excluded based on Exclusion #17 - Presence of haemodynamically significant mitral and/or aortic valve disease	-124	7,156	-43	3,804	-246	8,366
Excluded based on Exclusion #19a - History of active inflammatory bowel disease (IBD)	-18	7,138	-12	3,792	-37	8,329
Excluded based on Exclusion #19b - Active duodenal/gastric ulcers	-13	7,125	-8	3,784	-25	8,304
Excluded based on Exclusion #19c - Evidence of hepatic disease	-173	6,952	-80	3,704	-265	8,039
Excluded based on Exclusion #19d - Current treatment with cholestyramine or colestipol resins	0	6,952	0	3,704	-4	8,035
Excluded based on Exclusion #21 - Ivabradine use	-6	6,946	-10	3,694	-4	8,031
Final cohort		6,946		3,694		8,031

\* The Medicare data cut included all patients with a diagnosis for HF, stroke, or diabetes.

† Algorithm provided in Desai et al. (2018).

## 6 Variables

### 6.1 Exposure-related variables:

#### Study drug:

The study exposure of interest is initiation of sacubitril/valsartan (ARNI) at any dose and frequency. Initiation will be defined by no use of sacubitril/valsartan during the prior 180 days before treatment initiation (washout period). Patients are required to be incident users with respect to their exposure group only, since one of the RCT inclusion criteria was prior treatment with ACEi or ARB.

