#### Comparator agents:

Initiators of ACEi, any dose and frequency.

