## 9. Balance Assessment

Optum- <https://bwh-dope.aetion.com/projects/details/1069/results/63131/result/0>

MarketScan- <https://bwh-dope.aetion.com/projects/details/1072/results/63129/result/0>

Medicare- <https://bwh-dope.aetion.com/projects/details/1073/results/63128/result/0>

Date conducted: 12/22/2020

After review of initial feasibility and power analyses, complete creation of the remaining covariates from Section 6.2. Again, using the

dummy outcome of a 90-day gap in database enrollment, complete a 1:1 PS-matched analysis. The PS should include the complete list of covariates.

- Provide plot of PS distributions stratified by treatment group.

Note- Please refer to **Appendix B**.

- Report covariate balance after matching.

Note- For Table 1, please refer to **Appendix B**.

- Report reasons for censoring by treatment group.

	Overall	Referent	Exposure
Dummy outcome	0 (0%)	0 (0%)	0 (0%)
Death	150 (2.47%)	64 (2.11%)	86 (2.84%)
Start of an additional exposure	309 (5.09%)	106 (3.49%)	203 (6.69%)
End of Index Exposure	2285 (37.67%)	1206 (39.76%)	1079 (35.58%)
Specified date reached	1868 (30.79)	879 (28.98%)	989 (32.61%)
End of patient enrollment	696 (11.47%)	366 (12.07%)	330 (10.88%)
Switch to ARBs or Aliskiren + Nursing Home admission Occurred	758 (12.50%)	412 (13.58%)	346 (11.41%)

- Report follow-up time by treatment group.

Patient Group	Optum Median Follow-Up Time (Days) [IQR]	MarketScan Median Follow-Up Time (Days) [IQR]	Medicare Median Follow-Up Time (Days) [IQR]
Overall Patient Population	118 [58, 286]	139 [59, 296]	102 [46, 189]
Referent - ACE Inhibitors	126 [60, 309]	142 [77, 295]	102 [42, 170]
Exposure - Sacubitril/Valsartan	108 [56, 266]	136 [58, 300]	106 [58, 218]

- Report overall risk of the primary outcome.

	Optum	MarketScan	Medicare	Pooled
Risk per 1,000 patients	206.6	160.3	248.0	215.3

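### As written, the 180-day sacubitril/valsartan washout covers the exposed arm only, so patients who recently stopped the study drug can enter the ACE-inhibitor comparator arm

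*Protocol*

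**What the plan says.** Section 5.2 defines newness separately for each arm. For the exposed arm: "New users (defined as no use of sacubitril/valsartan in 180 days prior to index date) of the exposure will be identified". For the other arm: "New users of a comparator drug were identified as patients with no ACEi fills during the 60 days prior to the index date". The ACEi condition is meant to admit patients who change ACE inhibitor or restart after a short gap.

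Section 6.1 makes the principle explicit: "Patients are required to be incident users with respect to their exposure group only". Its reason is that prior ACEi or ARB treatment was an inclusion criterion of the randomised trial. The comparator is described only as "Initiators of ACEi, any dose and frequency".

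The Section 5.3 flowchart has a row "Excluded due to prior use of exposure", which removes 29,778 (Optum), 12,511 (MarketScan) and 33,013 (Medicare) patients, and a row "Excluded because patient qualified in >1 exposure category", which removes 8, 3 and 9. Neither says which arm it covers.

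**The concern.** The reason in Section 6.1 runs in one direction. Exposed patients must be allowed prior ACEi because the emulated trial required an ACEi or ARB beforehand. Nothing in it calls for controls who have recently taken the study drug.

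A comparator who took S/V within the past 180 days and then began an ACE inhibitor has been selected by whatever ended the S/V treatment, whether tolerability, cost, clinical course or another cause. Such a patient is not a new user in the active-comparator sense. Their event rate could differ from that of other comparators for reasons unrelated to the ACE inhibitor. No covariate legible in Appendix B records prior S/V, so the balance tables would not reveal them. The quantity at stake is the primary hazard ratio, which is to be compared with the trial's 0.80.

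**Working it through.** **1. The two rules side by side (Sections 5.2 and 6.1)**

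| Arm | Washout for own drug | Washout for the other drug |
|---|---|---|
| S/V | No S/V in 180 days | None; reason given |
| ACEi | No ACEi fill in 60 days | None stated; no reason given |

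No inclusion or exclusion criterion in Appendix A fills the lower right cell.

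**2. Does the flowchart fill it?** The row names no arm, so its neighbour, the row for prior use of the referent, is the best guide.
- In the matched cohort (Appendix B), exposed patients with baseline ARB use number 127 + 92 + 81 = 300. At least 3,033 − 300 = 2,733 (90%) had none.
- Under inclusion 5a those patients needed ACEi supply in days −47 to −2, inside the 60-day window. A referent washout applied to both arms would have removed them, unless the supply came from a fill more than 60 days before index.
- So the referent row looks arm-specific, which is also what Section 6.1 says. This does not prove the same for the S/V row.
- The flowchart also describes a different pool. The feasibility cohort (Section 7) has 4,217 + 2,218 + 6,293 = 12,728 comparators; Appendix B before matching has 46,268.

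**3. Does inclusion 5a close the route?** Comparators with baseline ARB use number 570 + 340 + 804 = 1,714 of 46,268 (3.7%) before matching and 118 + 89 + 75 = 282 of 3,033 (9.3%) after. The rest needed ACEi supply in days −47 to −2. That does not rule out S/V earlier in the 180 days. It also sits badly with the rule of no ACEi fill in 60 days. For Optum, 17,244 − 570 = 16,674 comparators (96.7%) are in this position.

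**4. Does movement between the drugs occur?** In Section 9, the censoring row "Start of an additional exposure" holds 203/3,033 = 6.69% of exposed and 106/3,033 = 3.49% of referent patients. Section 6.3.2 lists switching between arms as a censoring event.

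**5. Possible size.** Let p be the share of comparators with recent S/V use and r their hazard relative to other comparators. The comparator hazard is multiplied by about 1 + p(r − 1), so

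observed HR ≈ true HR / [1 + p(r − 1)].

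Both p and r are assumptions; the protocol gives neither.

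| True HR 0.80 | r = 0.75 | r = 1.5 | r = 2 |
|---|---|---|---|
| p = 1% | 0.802 | 0.796 | 0.792 |
| p = 5% | 0.810 | 0.780 | 0.762 |

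For example, 0.80/(1 + 0.05 × 1) = 0.762. With a true HR of 1, r from 1.5 to 2 gives 0.995 (p = 1%, r = 1.5) to 0.952 (p = 5%, r = 2).

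**6. Power cost of the fix.** The plan's final pooled figure first: 2 × 3,033 × 0.21525 = 1,305.7 events, and Φ(½ √1,305.7 × |ln 0.8| − 1.96) = Φ(2.07) = 0.981, matching the stated 0.980850168. Dropping 6.7% of pairs, a share borrowed from step 4 only as an illustration, leaves 1,218.2 events and Φ(1.93) = 0.973.

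**The case against.** The strongest reply has four parts.

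- **The exclusion may already cover both arms.** The flowchart row names no arm, so prior S/V users may have been removed throughout. This stands as a possibility: a reader might infer that such comparators are known to be in the cohort, and the documents do not show that. But Section 6.1 says the opposite of a both-arm rule, so the text would still need correcting.
- **Inclusion 5a narrows the route.** Read with the 60-day ACEi washout, a direct switcher from S/V enters only if the valsartan within S/V counts as an ARB, or if an ARB was taken in between. That is a fair reading of the text. Appendix B does not fit it, however, because most comparators show no ARB use, and patients with recent ACEi supply could have used S/V before that. These passages have to be reconciled before the route can be judged.
- **Direction is not established.** A reader might infer that the hazard ratio is biased in favour of S/V. That requires former users to have more events than other comparators, which no document states; with r below 1 the sign reverses. The exclusions for past angioedema and for hypotension, renal dysfunction and hyperkalaemia within 30 days also remove some patients likely to have stopped for intolerance.
- **The 6.69% is not the contaminated share.** It counts exposed patients censored after index, not comparators with prior S/V. Since all matched exposed patients had baseline ACEi use, some of these events may be leftover ACEi refills. Nor does anything in the protocol show that propensity matching would select former S/V users preferentially.

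The second part limits how many patients could be affected, and the third and fourth limit what can be said about bias. None supplies a reason for leaving prior S/V unrestricted among comparators.

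**Conclusion.** The point holds as a defect in the eligibility rule. The protocol states an arm-specific washout, gives a reason that covers one arm only, and reports nothing that shows recent S/V users were kept out of the comparator arm. Whether any entered, and how many, cannot be determined from the protocol.

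The effect on the hazard ratio is therefore conditional. Under the assumed shares of 1-5% it runs from negligible (0.80 to 0.796) to moderate (0.80 to 0.762) for relative hazards of 1.5-2, and to 0.802-0.810 in the other direction at a relative hazard of 0.75. Bias towards S/V is plausible, not demonstrated. The change is worth making because it is specific and cheap and removes the question.

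**What to change.** 1. Amend Sections 5.2 and 6.1 so that no S/V dispensing in the 180 days before index is required in both arms. Keep the comparator's separate 60-day ACEi washout unchanged; wording that simply allowed prior ACEi in both arms would remove it and admit prevalent ACEi users as controls.
2. In the Section 5.3 flowchart, state which arm each washout row covers.
3. Report, by database, how many comparators the added condition removes. If the row already covered both arms, say so and correct Section 6.1.
4. Reconcile the 60-day ACEi washout with inclusion 5a and the Appendix B counts. State whether 5a may be met by supply from a fill before the 60-day window, and whether valsartan within S/V counts as an ARB.

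Cost: one added condition, a rerun of the matching, and probably a small loss from a large comparator pool. Even losing 6.7% of matched pairs would leave pooled power at about 0.97 for a hazard ratio of 0.80.
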